17.3 Exploratory biomarkers

Exploratory biomarkers will be reported under a separate report, if analyzed.

18.0 Safety Analyses

18.1 Safety Variables

The following safety variables will be summarized:

- AEs
- Vital Signs

- o Supine Blood Pressure
 - Systolic Blood Pressure (SBP)
 - Diastolic Blood Pressure (DBP)
- o Pulse Rate
- Tympanic Body Temperature
- Respiratory Rate
- Electrocardiograms (ECG)
 - o Heart Rate
 - o RR Interval
 - o PR Interval
 - o QRS-Duration
 - QTc (Fridericia) Interval
 - ST Segment Assessment
 - T-Wave Assessment
 - o U-Wave Assessment
- Clinical Laboratory Evaluations
 - Clinical Chemistry
 - o Hematology
 - Urinalysis
 - Coagulation
- Physical Examination
- Evaluation of Infusion Site

18.1.1 Adverse Events

All AE summaries will include only treatment-emergent adverse events (TEAE). TEAEs are those starting or increasing in severity on or after the first dose of study drug.

TEAEs occurring following dosing in a specific period but before dosing in the next period will be attributed to that specific period. If the time is missing for an AE on a dosing day then the AE will be attributed to the treatment given on that day.

A TEAE overview table will be included, presenting the number and percentage of subjects reporting TEAEs, subjects reporting TEAEs with outcome=Death, subjects reporting serious TEAEs, subjects who discontinue study drug due to a TEAE, subjects reporting treatment related TEAEs, subjects reporting injection site reactions.

A breakdown of the number of AEs, number and percentage of subjects reporting each AE, categorized by body system and preferred term coded according to the latest version of Medical Dictionary for Regulatory Activities (MedDRA), will be presented by part, treatment and also M254 overall. Subjects will only be counted once within each body system or preferred term. There will be one such table presented for:

- All TEAEs
- TEAEs considered related to study drug
- Serious AEs (SAEs)
- AEs of Special Interest (AESI: systemic and local reactions, hemolysis, infections, flu-like symptoms, rash, myalgia and arthralgia, fever, chills)
- Severe AEs.

A summary of AEs reported, categorized by relationship (categories: related, not related) will also be provided by part, treatment and also M254 overall. AEs reported in the eCRF as 'Possibly', 'Likely' and 'Definitely' will be considered related to study drug, while categories 'None' and 'Unlikely' will be considered not related.

A summary of AEs reported, categorized by severity as recorded on eCRF, will also be provided by part, treatment and also M254 overall.

All AEs recorded on the eCRF will be listed together with MedDRA coding. One listing will contain TEAEs and one listing will contain non-treatment-emergent AEs.

A listing of AEs leading to study drug discontinuation will be provided ('Adverse Event' is reported as primary reason for early termination/study non-completion).

The following missing data will be imputed as defined (for calculations only / will not be presented):

- Missing AE start and / or end times for the calculation of onset and duration will be assumed to be at 00:01 for a start time and 23:59 for end times
- Missing AE severity or relationship will be assumed to be severe or related, respectively
- Missing AE start times for the determination of treatment emergence will be assumed to occur after treatment unless partial date documents the AE as happening prior to treatment
- Missing AE start times for the determination of treatment assignment will be assumed to occur after treatment on the recorded date one minute after dosing
- Missing AE start date will be assumed to be after treatment for the determination of TEAE and on treatment for single treatment studies but will not be attributed to treatment in studies with multiple treatments

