# 7 DISCONTINUATION OF STUDY INTERVENTION AND PARTICIPANT DISCONTINUATION/WITHDRAWAL

## 7.1 Discontinuation of Study Intervention

In accordance with the Declaration of Helsinki, International Council for Harmonisation (ICH) GCP Guidelines, and the US FDA Regulations, a research subject has the right to withdraw at any time for any reason without prejudice to future medical care. However, in the absence of a medical contraindication, the Investigator should encourage the subject to remain in the study and, at a minimum, follow the subject for safety data collection.

Compound: M254 Protocol: MOM-M254-001

Protocol Date and Version:8 Global 28 April 2020

The Sponsor and Investigator also have the right to withdraw participants. Subjects or patients may be discontinued from study treatment if they experience intolerable toxicity related to any study treatment despite dose reduction, or for any of the following reasons:

- Withdrawal of subject informed consent
- AE
- Significant noncompliance with protocol requirements
- Need for prohibited therapy
- Termination of the study
- Any other reason which, in the opinion of the Investigator or Sponsor, would justify the subject's removal
- Subject lost to follow-up

All reasons for early termination or withdrawal will be documented in the eCRF.

The Sponsor and the Investigator may decide to halt dosing for safety reasons, including emerging nonclinical data, clinically relevant AEs, or relevant data from other sources indicating safety concerns.

Termination of the study by the Sponsor may take place upon written notice to PRA Netherlands for the following reasons: 1) if the Ethics Committee irrevocably revokes approval for the study; 2) if it is necessary to protect the safety, health, or welfare of participants; 3) if it transpires that continuation of the study cannot serve any scientific purpose, and this is confirmed by the Ethics Committee; 4) if conducting the study becomes prohibitive by law, rule, regulation, or any amendment thereof; or 5) if the Investigator is no longer capable of performing the tasks of the Investigator, and no replacement agreeable to both parties can be found.

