Most systemic infusion reactions are either acute or subacute, occurring within 24 hours of the infusion. Delayed reactions are less common; by definition these occur more than 24 hours after the infusion; in practice most occur 5 to 10 days after the infusion [25]. Infusion reactions are often described in terms that are related to a presumed mechanism (eg, allergic, IgE mediated, immune complex mediated, target-engagement mediated, cytokine release, anaphylactic, anaphylactoid); in practice, determination of mechanism is often challenging and based on observation, course, laboratory assessments, and expertise. Acute infusions should be classified as mild moderate or severe. Mild reactions may present with flushing, dizziness, diaphoresis, nausea, palpitations, and hyperemia. Moderate reactions may present with chest pain, hypertension, hypotension, fever, urticaria, dyspnea, chills, and/or rash. Severe reactions may present with marked hypertension or hypotension, severe dyspnea, bronchospasm, stridor, wheezing, and rigors. Most reactions tend to be mild, and related to the rate of the infusion [25], and can be managed by slowing or temporarily stopping the infusion. If necessary, antihistamines or acetaminophen may be given according to the clinical judgment of the Investigator. With moderately severe acute reactions, the infusion should be discontinued, and the subject should be treated with acetaminophen and antihistamines, and if necessary with corticosteroids. Once the reaction has been arrested, the infusion may be cautiously restarted, if deemed appropriate by the Investigator. With severe reactions the infusion should be discontinued, and the subject should be treated immediately with acetaminophen, antihistamines, and systemic corticosteroids. If anaphylaxis if present, epinephrine should be administered before the corticosteroids. The infusion should not be restarted even if the reaction is brought under control.

Delayed reactions (after 24 hours) most likely represent a mild type III immune complex reaction, typically secondary to anti-drug antibodies. The most common symptoms that have been reported associated with delayed reactions include joint pains, rash, arthritis, myalgia, jaw pain, fatigue, headaches, edema, sore throat, and fever. If the symptoms are mild, acetaminophen alone may be sufficient. Persistent severe symptoms may require a short course of corticosteroids, and discontinuation of further study drug administration.

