# 10.3.3 Recording and Follow-up of AE and/or SAE

#### AE and SAE Recording

- When an AE/SAE occurs, it is the responsibility of the Investigator to review all documentation (eg, hospital progress notes, laboratory reports, and diagnostics reports) related to the event.
- The Investigator will then record all relevant AE/SAE information in the case report form (CRF).
- It is **not** acceptable for the Investigator to send photocopies of the participant's medical records to Sponsor in lieu of completion of the AE/SAE CRF page.
- There may be instances when copies of medical records for certain cases are requested by Sponsor. In this case, all participant identifiers, with the exception of the participant number, will be redacted on the copies of the medical records before submission to Sponsor.
- The Investigator will attempt to establish a diagnosis of the event based on signs, symptoms, and/or other clinical information. Whenever possible, the diagnosis (not the individual signs/symptoms) will be documented as the AE/SAE.
- The Investigator must assign the following AE attributes:
  - Adverse event diagnosis or syndrome(s), if known (if not known, signs or symptoms);
  - Dates of onset and resolution (if resolved);
  - Intensity (or toxicity defined below);
  - Assessment of relatedness to investigational product; and
  - Action taken. Changes in AE severity are to be recorded as a single event worst severity.

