15.0 Treatment Compliance and Exposure

Study drug administration data will be listed, including date, start and end times of infusion, amount, volume, infusion completion / interruption details and comments.

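### SAP 18.1.1 selects its listing of AEs leading to study drug discontinuation by the reason for leaving the study, so the listing can misclassify patients in both directions

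*SAP*

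**What the plan says.** SAP 18.1.1 states that "A listing of AEs leading to study drug discontinuation will be provided" and gives the selection rule in parentheses: "Adverse Event' is reported as primary reason for early termination/study non-completion". Earlier in the same section, the TEAE overview table has a row for "subjects who discontinue study drug due to a TEAE". No derivation is attached to that row.

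The protocol has text on stopping drug and on leaving the study:

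- Section 7.1, on discontinuing study intervention, says that unless medically contraindicated "the Investigator should encourage the subject to remain in the study and, at a minimum, follow the subject for safety data collection".
- Section 8.3.5 says of severe infusion reactions: "The infusion should not be restarted even if the reaction is brought under control". For delayed reactions with persistent severe symptoms it foresees "discontinuation of further study drug administration". Neither statement requires study withdrawal.
- Appendix 5 pairs stopping study intervention for liver findings with continued monitoring.
- Section 7.2 says that a participant who leaves the study is also permanently off study intervention. It does not state the converse.

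Two relevant data items are already collected. Protocol 10.3.3 requires, for each AE, "Action taken. Changes in AE severity are to be recorded as a single event worst severity". SAP 15.0 lists drug administration data, including "infusion completion / interruption details and comments".

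**The concern.** The listing's title is about drug and its criterion is about the study. Where the protocol lets a patient stop drug and stay for follow-up, the criterion can fail to select exactly the events the title promises. It can also select patients whose dosing was never cut short.

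Safety and tolerability is the primary objective of Parts A, B and D, and safety is one of the primary objectives of Part C. A reader of the study report would use this listing to see which events made dosing untenable. Patients retained for follow-up, as Section 7.1 encourages, are the ones most likely to be missing from it.

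**Working it through.** The plan gives no figure to reproduce. The check sets the SAP's selection rule against the protocol's definitions and follows individual patients through both.

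**Inputs**

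- Selection rule: AE as the primary reason for early termination or non-completion (SAP 18.1.1).
- Completion: a participant has completed the study after going through all its phases, including the last visit or last scheduled procedure (Protocol 4.4.1).
- Follow-up after dosing: 28 days after each infusion in Parts B and C, and at least 28 days after the last dose in Part D (Protocol 4.1.2 to 4.1.4).

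**Cases**

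| Patient | Drug stopped for an AE? | AE the primary reason for leaving? | In the listing? |
|---|---|---|---|
| Part B or C: second-period infusion permanently stopped for a severe reaction; final follow-up attended | Yes | No; meets the 4.4.1 definition of completion | Can be left out |
| Part D: last planned infusion permanently stopped for an AE; final follow-up attended | Yes | No, for the same reason | Can be left out |
| Any part: drug stopped for an AE; patient later leaves with consent withdrawal recorded as the main reason | Yes | No, because of the word primary | Left out |
| Part C: both infusions received in full; patient leaves before the last visit because of an AE | No | Yes | Wrongly included |
| Part B or C: first-period infusion stopped for an AE; second period not given | Yes | Possibly | Possibly captured |
| Part D: dosing stopped after dose 2 for an AE; patient followed to the last visit | Yes | Depends on the eCRF | Cannot be determined |

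An infusion that is paused and restarted is not a discontinuation and is outside the point.

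The first two rows are the clearest misses, because no planned dose remains whose omission could be recorded as non-completion. The fourth row is the clearest false inclusion.

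**Scale, only if the same rule is used for the overview row**

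The change from one misclassified patient is 1/n:

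- Part D, n = 34: 1/34 = 2.9 points
- Part D, n = 15: 1/15 = 6.7 points
- One Part C cohort, n = 10: 1/10 = 10 points
- Part C overall, n = 20: 1/20 = 5 points

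**Placement**

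The listing is missing from SAP Appendix 4. Section 16.2.6 there names only treatment-emergent and non-treatment-emergent AE listings, with concomitant medications. The overview table (Table 14.3.1.1) is scheduled for the interim reports after Part B and after Part C Cohort 1. The later statement of deviations from the SAP, in the statistical methods appendix, records no change to the rule.

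**The case against.** Most of the case on the other side limits the point rather than removing it.

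- **The rule is attached to the listing only.** A reader might infer that the reported discontinuation rate is understated, or could read zero despite toxicity. The SAP does not say so: the overview row is specified separately, and a listing has no rate. This limit stands.
- **Non-completion is part of the rule.** A reader might infer that a Part D patient stopped after dose 2 counts as no discontinuation. Under Protocol 4.4.1 the missed doses could be recorded as non-completion with AE as the reason, so that example is not established. This also stands.
- **The events are not lost.** A reader might infer that these AEs go unreported. SAP 18.1.1 lists all AEs recorded on the eCRF, systemic reactions also enter the special-interest table, and stopped infusions appear in the administration listing.
- **Early termination might include termination of treatment.** Section 7.1 uses the phrase in a section about study intervention, and the eCRF is not available to settle it. But the SAP pairs the phrase with study non-completion, so the disposition reading is the natural one.
- **The protocol partly couples the two events.** Section 7.2 lets the investigator withdraw a patient from the study for a treatment-related AE of Grade 3 or higher. The wording is permissive, so a patient can still be kept for follow-up. The Section 7.1 sentence on staying in the study follows a statement of the right to withdraw; it is general encouragement, not a rule written for AE-driven stops.
- **A stopped infusion is not always drug discontinuation.** Section 8.3.5 speaks of that infusion, and later dosing might continue. This is fair, and such cases need their own category.
- **Discontinuation is not an endpoint.** The primary safety endpoints are AE incidence and severity, and clinically significant changes in laboratory tests, vital signs and ECGs. This lowers the severity.

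**Conclusion.** As written, the rule does not match the listing's title and can misclassify in both directions. It can omit a patient whose last infusion was permanently stopped for an AE and who completed follow-up. It would include a patient who received every planned infusion and later left because of an AE.

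The effect established by the documents is on classification within one listing. The 2.9 to 6.7 points per patient in Part D are conditional on the same rule being applied to the overview row, which the SAP leaves undefined. The documents do not support a claim that a discontinuation rate has been understated.

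The omission rests on two assumptions: that a last planned infusion permanently stopped for an AE is meant to count as drug discontinuation, and that the eCRF records a patient who attends the final follow-up as a completer. Severity is minor.

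**What to change.** In SAP 18.1.1, replace the parenthetical rule as follows:

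1. Derive both the listing and the overview row from the AE-level action-taken attribute, selecting TEAEs for which study drug was permanently discontinued. Use the eCRF's actual category name, which neither document shows.
2. Cross-check against the infusion completion and interruption record in SAP 15.0, and resolve mismatches before database lock.
3. Show permanently stopped infusions as a separate category where later dosing continued.
4. Report AE as the primary reason for leaving the study separately, under disposition (SAP 11.0), which already breaks down withdrawals by reason.
5. Add the listing to Appendix 4, section 16.2.6.

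The cost is a wording change, one derivation from data already collected, and one listing, provided the eCRF has a usable action-taken category. If outputs are already final, the same derivation can support a corrected listing or a clarifying note in the study report; SAP 3.0 allows significant changes to be documented there without an updated SAP.

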## 9.5 Handling of Missing Data

In general, there will be no substitutions made to accommodate missing data points. All data recorded on the CRF will be included in data listings that will accompany the CSR.

For AEs, missing dates will not be imputed; however, if partial dates are available, they will be used to assess if the AE occurred during the treatment period. Missing severities of AEs

Compound: M254 Protocol: MOM-M254-001

Protocol Date and Version:8 Global 28 April 2020

will not be imputed and will be considered missing in any tabulations of AE severity. If an AE is missing a response to the question regarding relationship to treatment, the event will be considered to be related.

No other data imputation will be performed.

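### In Parts B and C an adverse event with no start date falls out of both the M254 and IVIg counts, and the SAP's missing-severity rule departs from the protocol without being declared

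*SAP*

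**What the plan says.** AE incidence and severity is a primary endpoint in every part (SAP 5.1.1). In Parts B and C each patient is planned to receive both M254 and IVIg, so each AE has to be assigned to a period.

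**Start date.** SAP 18.1.1 says "Missing AE start date will be assumed to be after treatment for the determination of TEAE". The same bullet counts such an AE as on treatment in single-treatment studies, but says it "will not be attributed to treatment in studies with multiple treatments". Protocol 9.5 does not say which treatment an undated AE belongs to. On incomplete dates it says that "if partial dates are available, they will be used to assess if the AE occurred during the treatment period".

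**Severity and relationship.** SAP 18.1.1: "Missing AE severity or relationship will be assumed to be severe or related, respectively". Protocol 9.5 says that missing severities "will not be imputed and will be considered missing in any tabulations of AE severity". For an AE "missing a response to the question regarding relationship to treatment, the event will be considered to be related", so on relationship the two documents agree.

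**Tables.** SAP 18.1.1 presents AEs by part, by treatment and for M254 overall. The Part B and C layout in SAP 9.5 has an M254 period, an IVIg period and their difference. The pooled layout has M254 dose levels, M254 total and IVIg. Neither has a column for unassigned events.

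**Declared changes.** SAP 3.0 undertakes to identify considerations that differ substantially from the protocol. SAP 7.1 lists one change, to the definition of a therapeutic platelet count.

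**The concern.** An event that the SAP itself classes as treatment-emergent has no column in the table meant to count treatment-emergent events by treatment. The M254 and IVIg columns can then both look cleaner than the data, and the reader of the table cannot see that anything was left out.

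The severity point is different in kind. The SAP grades as severe an event that nobody graded, where the protocol would report the grade as missing. The SAP also summarises severity as entered on the case report form, and says its imputations serve calculations and are not displayed. It never says which AE outputs use the imputed grade. The AE dataset is classed as critical and double-programmed (SAP 9.2.4.1), so the specification needs to admit only one reading.

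**Working it through.** The plan states no figure for this point, so there is none to reproduce. The check sets the rules side by side and then works out what one incomplete record can do.

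**1. The rules compared**

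| Missing item | Protocol 9.5 | SAP 18.1.1 | Result |
|---|---|---|---|
| Relationship | related | related | agree |
| Severity | stays missing | severe | conflict, not declared in SAP 7.1 |
| Start date: which treatment? | silent | none, if multiple treatments | no protocol breach, but no column in the tables |
| Partial date: treatment-emergent? | used to judge whether in the treatment period | used to rule out onset before treatment (start-time bullet) | similar |
| Partial date: which period? | no rule stated | no rule stated | gap |

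**2. Could the period often be recovered?** The second infusion is given on Day 29 at the earliest, and weekly platelet monitoring can run to 56 days after the first (Protocol 4.1.2, 4.1.3). AEs are assessed at every visit in the Part B and C schedules. An AE that was first reported, or had ended, before the second infusion must have started earlier, so it cannot belong to the second period. The SAP does not use this information to choose a period.

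**3. Effect on incidence**

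Inputs: Part C has 10 patients per cohort and 20 in total; Part B has 2 per planned cohort and 4 × 2 = 8 in the planned cohorts. The number of incomplete records is not in the documents, so k = 1 to 3 affected patients is an assumption.

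Shift in a column's incidence per affected patient = 100 × 1/n percentage points:

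- Part C total: 100/20 = 5
- Part C cohort: 100/10 = 10
- Part B planned total: 100/8 = 12.5
- Part B cohort: 100/2 = 50

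These shifts need a patient with no other AE in that column. Otherwise the patient is already counted and the shift in patients with any AE is zero. The count of events, which SAP 18.1.1 also reports, loses one for each undated event either way.

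For context, exact 95% intervals:

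- n=10: 0/10 gives 0 to 30.8%; 1/10 gives 0.3 to 44.5%.
- n=20: 0/20 gives 0 to 16.8%; 1/20 gives 0.1 to 24.9%.

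**4. Effect on the M254 minus IVIg difference**

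Putting all k affected patients under M254, then all under IVIg, moves the reported difference by +100k/n and −100k/n points:

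| k | Part C cohort (n=10) | Part C total (n=20) |
|---|---|---|
| 1 | ±10 | ±5 |
| 2 | ±20 | ±10 |
| 3 | ±30 | ±15 |

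The range is symmetric because nothing says which period the events came from.

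**5. Effect on severe events**

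With s events recorded as severe and m ungraded, the protocol gives s. The SAP gives s + m in any table that uses the imputation. For s = 1 and m = 1, 2, 3 that is 1 against 2, 3, 4. Which tables these are is unclear: SAP 18.1.1 names a table of severe AEs, but the output list in SAP Appendix 4 contains none.

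**The case against.** The strongest reply is that this will rarely matter. Investigators must record onset date and intensity for every AE (Protocol 10.3.3), AEs are reviewed at each visit, and data problems go back to data management (SAP 8.2). The documents show no incomplete AE record. All AEs remain in the listings, and deaths and other SAEs are listed by subject, so nothing disappears from the report. The SAP also states that it supersedes the protocol's statistical considerations, so only one rule governs. All of this stands as an argument about size. It does not supply the missing column, say which tables use the imputed grade, or show that replacing a missing grade in a primary endpoint is too minor to declare.

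A reader might also infer several stronger things that the documents do not support:

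- *The rule favours M254.* An undated AE is absent from both columns and could belong to either period. Absolute incidence is understated, but the direction of the effect on the comparison is unknown.
- *The SAP ignores partial dates.* It uses them for treatment emergence. What it lacks is a rule for choosing between periods.
- *The whole quoted sentence contradicts the protocol.* Only the severity half does.
- *The severity table will show ungraded events as severe.* Read with its own wording on recorded severity, it need not. The defect is ambiguity.

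**Conclusion.** The point holds as a specification gap and an undeclared departure from the protocol. In Parts B and C, following SAP 18.1.1 as written removes an undated treatment-emergent AE from every treatment column of a primary safety table. The protocol is silent on attribution, so this breaks no protocol rule. The severity rule does conflict with Protocol 9.5. The later record of deviations from the SAP (Statistical Methods and Analysis Output, section 2) does not mention AE handling, so it does not settle either matter.

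The likely size is small. One affected patient is worth 5 points in Part C overall or 10 points in a Part C cohort, provided that patient has no other AE in the column and all planned patients are dosed in both periods. How many such records exist is not stated, and it may be none.

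**What to change.** In SAP 18.1.1:

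1. Assign an AE with a missing or partial start date to a period from its partial date, end date or first-reported visit, where these settle the matter.
2. Show the remaining AEs in a 'not attributable' row or column, and add a bounding sensitivity analysis that assigns them to M254 and then to IVIg. This is preferable to counting undetermined events under M254 by default, which would build a direction into the comparison that the data do not support.
3. Tabulate missing severity in its own row, as Protocol 9.5 provides, with 'assumed severe' as a sensitivity line. Alternatively, keep the imputation, declare it in SAP 7.1 and state which tables use it.
4. Report how many records each rule affected.

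The missing-relationship rule needs no change. The cost is a few lines of SAP text, minor programming and one extra table row.
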